1. PROTOCOL SUMMARY

1.1 Schedule of activities (SoA)

The procedures for the screening and treatment periods in this study are presented in Table 1 and Table 2, and the procedures for the follow-up period are presented in Table 2. Patients who continue beyond Cycle 13 will continue with all Cycle 13 assessments until termination of treatment (Table 1).

Whenever vital signs and blood draws are scheduled for the same nominal time, the assessments should occur in the following order: vital signs and then blood draws. The timing of the vital signs assessments should be such that it allows the blood draw to occur at the timepoints indicated in the SoAs. Whenever electrocardiograms (ECGs), vital signs, and blood draws are scheduled for the same nominal time, the assessments should occur in the following order: ECG, vital signs, and then blood draws. The timing of the first 2 assessments should be such that it allows the blood draw to occur at the timepoints indicated in the SoAs.

For durvalumab

- Patients may delay dosing under certain circumstances.
 - Dosing may be delayed per the Dosing Modification and Toxicity Management Guidelines, due to either an immune or a non-immune-related AE.
 - If dosing must be delayed for reasons other than treatment-related toxicity, dosing will resume as soon as feasible.
 - Dosing intervals of subsequent cycles (during chemotherapy interval is 21 days, post chemotherapy interval is 28 days) may be adapted +/-3 days as clinically feasible in order to gradually align treatment cycles with the schedule of tumor efficacy (RECIST) and PRO assessments.

For EP treatment

- Patients may delay and subsequently resume dosing per local standard clinical practice.
 - If dosing must be delayed for reasons other than treatment-related toxicity, dosing will occur as soon as feasible.

Table 1 Schedule of assessments for durvalumab therapy treatment

		During Chemotherapy 1 cycle = 21 days				Post-Chemotherapy 1 cycle = 28 days				
	Screening	C1	C2	C3	C4-C6	C5-C7 to PD		End of treatment		
Week	-4 to -1	0	Q3w ±3 days during chemotherapy and q4w ±3 days post-chemotherapy, unless dosing needs to be held for toxicity reasons							
Day	-28 to -1	1 ^a	Q21days ±3 days during chemotherapy and q28days ±3 days post-chemotherapy, unless dosing needs to be held for toxicity reasons							For details, see Section
Informed Consent										
Informed consent: study procedures ^b	X								5.1	

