8.2.7 Patient reported outcomes (PRO)

–PRO” is an umbrella term referring to all outcomes and symptoms that are directly reported by the patient. PROs have become a significant endpoint when evaluating effectiveness of treatments in clinical studies. The following PROs will be administered in this study: EORTC QLQ-C30 v3 (core questionnaire), EORTC QLQ-LC13 (lung cancer module), patient-reported outcomes version of the CTCAE (PRO-CTCAE). (see [Appendix H and I](#)).

The PRO instruments will be completed by the patients using a paper format questionnaire on day 1 of every cycle. All assessments should be completed without assistance from anyone according to the assessment schedules. It takes approximately 30 minutes for patients to complete the questionnaires; therefore, the burden to the patient is moderate.

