PFS (days) = Date of event or Censor date – treatment start date +1

Patients who have not progressed or died at the time of analysis will be censored at the time of the latest date of assessment from their last evaluable assessment. However, if the patient progresses or dies after 2 or more missed visits, the patient will be censored at the time of the latest evaluable assessment prior to the 2 missed visits. If the patient has no evaluable visits or does not have baseline data, he/she will be censored at Day 1 unless he/she dies within 2 visits of baseline, in which case the date of death is the event date.

OS: Defined as the time from the first date of treatment until death due to any cause.

OS (days) = Death date or Censor date - treatment start date +1

Any patient not known to have died at the time of analysis will be censored based on the last recorded date on which the patient was known to be alive.

ORR: Based on Investigator–assessed response to treatment of CR and PR, per RECIST1.1.

DoR: Defined as the time from the date of first documented response per RECIST1.1 until the first date of documented progression per RECIST1.1 or death in the absence of disease progression.

DoR (days) = Date of PFS event or censoring – Date of first response +1

The end of response should coincide with the date of progression or death from any cause used for the PFS endpoint. If a patient does not progress following a response, then the patients' DoR will be censored at the PFS censoring time. DoR will not be defined for those patients who do not have a documented response.

Time to symptom deterioration (EORTC QLC-C30 and QLC-LC13): Defined as the time from start of study drug until the date of the first clinically meaningful symptom deterioration that is confirmed at the subsequent assessment or death (by any cause) in the absence of a clinically meaningful symptom deterioration, regardless of whether the patient withdraws from study drug or receives another anticancer therapy prior to symptom deterioration.

Change from baseline (EORTC QLC-C30 and QLC-LC13, PRO-CTCAE): Defined as the post-treatment value minus the value at baseline. The % change from baseline will be calculated as (postbaseline value - baseline value) / baseline value x 100.

Treatment duration: Defined as Treatment end date - Treatment start date +1; will be summarized.

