#### Endpoints analyzed:

- Progression-free survival (PFS): This analysis will be performed for the Intention-to-Treat population (ITT). PFS is defined as the time from the first date of treatment until the date of objective disease progression or death (by any cause in the absence of progression) regardless of whether the patient withdraws from IP or receives another anticancer therapy prior to progression.

**PFS (days)** = Date of event or Censor date – treatment start date +1

Patients who have not progressed or died at the time of analysis will be censored at the time of the latest date of assessment from their last evaluable assessment. However, if the patient progresses or dies after 2 or more missed visits, the patient will be censored at the time of the latest evaluable assessment prior to the 2 missed visits. If the patient has no evaluable visits or does not have baseline data, he/she will be censored at Day 1 unless he/she dies within 2 visits of baseline, in which case the date of death is the event date.

The PFS analysis will be based on the programmatically derived RECIST 1.1 using the Investigator tumor assessments. It will be analysed PFS, PFS at 6 months (6mPFS) and PFS at 12 months (12mPFS).

- Objective response rate (ORR): This outcome will be analysed for the responder's analysis set. The ORR will be based on the programmatically derived RECIST 1.1 using the investigator tumor data.
- Duration of response (DoR): This outcome will be analysed for the responder's analysis set. DoR is defined as the time from the date of first documented response per RECIST1.1 until the first date of documented progression per RECIST1.1 or death in the absence of disease progression.

DoR (days) = Date of PFS event or censoring – Date of first response +1

The end of response should coincide with the date of progression or death from any cause used for the PFS endpoint. If a patient does not progress following a response, then the patients' DoR will be censored at the PFS censoring time. DoR will not be defined for those patients who do not have a documented response. It will be analysed DoR and DoR at 1 year (DoR12)

- Overall survival (OS): This analysis will be performed for the Intention-to-Treat population (ITT). OS is defined as the time from the first date of treatment until death due to any cause.

OS (days) = Death date or Censor date - treatment start date +1

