- Time to symptom deterioration: defined as the time from start of study drug until the date of the first clinically meaningful symptom deterioration (a decrease in the score from baseline of  $\geq 10$  points) that is confirmed at the subsequent assessment (at least 14 days apart) or death (by any cause) in the absence of a clinically meaningful symptom deterioration, regardless of whether the patient withdraws from study drug or receives another anticancer therapy prior to symptom deterioration. Death will be included as an event only if the death occurs within 2 visits of the last PRO assessment where the symptom change could be evaluated.  
Patients whose QoL (as measured by EORTC QLQ-C30) have not shown a clinically meaningful deterioration and who are alive at the time of the analysis will be censored at the time of their last PRO assessment where the QoL/function could be evaluated. Also, if QoL deteriorates after 2 or more missed PRO assessment visits or the patient dies after 2 or more missed PRO assessment visits, the patient will be censored at the time of the last PRO assessment where QoL/function could be evaluated. If a patient has no evaluable visits or does not have baseline data, he/she will be censored at Day 1.
- Time to quality of life/ function deterioration: defined as the time from start of study drug until the date of the first clinically meaningful deterioration (a decrease in the function scales or the global health status/QoL from baseline of  $\geq 10$  points) that is confirmed at the subsequent assessment (at least 14 days apart) or death (by any cause) in the absence of a clinically meaningful deterioration, regardless of whether the patient withdraws from study drug or receives another anticancer therapy prior to QoL/function deterioration. Death will be included as an event only if the death occurs within 2 visits of the last PRO assessment where the QoL/function change could be evaluated.
- Symptom improvement rate: defined as the number (%) of patients with 2 consecutive assessments at least 14 days apart that show a clinically meaningful improvement (an increase from baseline score  $\geq 10$  points for EORTC QLQ-C30 symptom scales/items) in that symptom from baseline.

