#### Endpoints analyzed:

- Change from baseline in European Organisation for Research and Treatment of Cancer Quality of Life Questionnaire Core 30 items (EORTC QLQ-C30) and Questionnaire-Lung Cancer 13 (EORTC QLQLC13):

Scores for the QLQ-C30 and QLQ-LC13 questionnaires will be calculated according to published scoring manuals or the developer's guidelines. Raw scores from scales in both questionnaires will be standardized by linear transformation so that they range from 0 to 100. Higher scores for symptom items indicate greater symptom severity, while higher scores for function and global health status/QoL items indicate better function and health status/QoL. For both questionnaires, a clinically meaningful change will be prespecified as an absolute change in score from baseline of  $\geq 10$  points (either deterioration or improvement). For the five key disease-related symptoms (cough, dyspnea, and chest pain [QLQ-LC13], and fatigue and appetite loss [QLQ-C30]), changes at each visit from baseline to disease progression or end of follow-up (whichever came first) will be analyzed using a mixed model for repeated measures (MMRM) to derive an overall adjusted mean change from baseline, reflecting the average treatment effect over visits. The model assumes PROs will be collected at multiple visits per

patient. Visits with >75% missing data will be excluded from the analysis. The MMRM included treatment, age at baseline (<65 vs ≥65 years), sex, smoking history (smoker vs non-smoker) and visit interaction as fixed factors, and baseline score as a covariate; the model further adjusted for baseline score-by-visit interaction.

Summaries of original and change from baseline values of each symptom scale/item, the global HRQoL score, and each functional domain will be reported by visit.

Time to symptom deterioration and time to quality of life / function deterioration (defined in 4.2.2) will be analyzed by product limit methods to provide summaries of the number and percentage of patients experiencing a clinically meaningful deterioration or death, the median time to deterioration together with the corresponding 95% CIs, as well as the Kaplan-Meier plot. An stratified log-rank test adjusted for therapy will be used with HR s and 95% CIs calculated using a stratified Cox proportional hazards model.

Symptom improvement rate and Quality of life / function improvement (defined in 4.2.2) will be summarized.

- Changes from baseline in PRO-CTCAE:

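### The PRO time-to-deterioration rule censors at Day 1 a patient who dies before any evaluable follow-up questionnaire, although death is an event and the parallel PFS rule counts it

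*SAP*

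**What the plan says.** SAP 4.2.2.2 defines time to symptom deterioration as time to the first confirmed deterioration "or death (by any cause) in the absence of a clinically meaningful symptom deterioration". It then limits the death component: "Death will be included as an event only if the death occurs within 2 visits of the last PRO assessment", and the sentence goes on to require that the symptom change could be evaluated at that assessment. The censoring paragraph ends: "If a patient has no evaluable visits or does not have baseline data, he/she will be censored at Day 1". Nothing is said about a patient in that position who has died.

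Protocol 9.5.2.3 gives the same rule twice, once for symptoms and once for QoL/function. It reaches the QLQ-LC13 as well: Protocol 9.5.2.3(b) handles that questionnaire as for the QLQ-C30, and SAP 4.2.2.2 lists time to symptom deterioration for it.

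The PFS rule uses nearly the same sentence but adds an exception. Protocol 9.4 has "unless he/she dies within 2 visits of baseline, in which case the date of death is the event date", and SAP 4.2.2.1 has "censored at Day 1 unless he/she dies within 2 visits of baseline, in which case the date of death is the event date".

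SAP 5.2.2 summarises the PRO endpoint by Kaplan-Meier curve, median with 95% CI, and "the number and percentage of patients experiencing a clinically meaningful deterioration or death". SAP 6.2 foresees no imputation, and no sensitivity analysis is planned that would restore these deaths.

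**The concern.** A patient can fill in the baseline questionnaire, start treatment and die before the next one is due. That patient has failed on a deterioration-or-death endpoint, and earlier than almost anyone else. The rule gives the patient a censored time of one day.

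The censoring is not independent of outcome, because the patient has no evaluable follow-up precisely because of the death. The direction of the error is therefore known: the early Kaplan-Meier curve is too high, there are too few events, and the median can only be too long or unchanged. The number-and-percentage summary is also too low, because these patients remain in its denominator as non-events.

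The same rule serves every QLQ-C30 symptom and function scale, global health status and the QLQ-LC13 symptoms, so one omission affects a whole family of reported curves.

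**Working it through.** **1. The two rules side by side**, for a patient with a baseline assessment, no evaluable follow-up and an early death:

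| Endpoint | Is death an event by definition? | No evaluable visits | Early-death exception | Result |
|---|---|---|---|---|
| PFS | Yes, any cause | Censored at Day 1 | Yes, within 2 visits of baseline | Event at date of death |
| PRO deterioration | Yes, any cause, within 2 visits of an assessment where change could be evaluated | Censored at Day 1 | None | Censored at Day 1 |

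**2. When the gap opens.** Protocol 8.2.7: "The PRO instruments will be completed by the patients using a paper format questionnaire on day 1 of every cycle". Protocol 1.1: "during chemotherapy interval is 21 days". The first follow-up questionnaire is therefore due about 21 days after the first dose, and a patient who dies before then is caught by the rule.

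**3. How many such deaths.** The documents give no figure, so these are assumptions scaled to survival figures that they cite. Use n = 85 and t = 21/30.4375 = 0.690 months.

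- Exponential, P = 1 − 0.5^(t/median). Median 13.0 months (Protocol 2.3.1.2): 3.6%, or 3.1 of 85. Median 11 months (upper end of the range in Protocol 2.3.3): 4.2%, or 3.6 of 85. Median 7 months (lower end): 6.6%, or 5.6 of 85.
- Weibull, S(t) = exp(−ln 2 × (t/13.0)^a), through the 13.0-month median and a landmark from Protocol 2.3.3. From 53.7% at 12 months, a = ln(−ln 0.537 / ln 2) / ln(12/13) = 1.36. From 33.9% at 18 months, a = 1.37. Either gives 1.2–1.3% dead by day 21, or about 1.1 of 85.

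The Weibull follows the cited figures better. An exponential with median 13.0 months predicts 0.5^(18/13) = 38.3% alive at 18 months, against the cited 33.9%. The hazard rises with time, so the exponential overstates early deaths in that population.

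**4. Effect on the curve.** Let k patients be censored at Day 1. The rule then estimates S_rest(t), the curve of the other 85 − k. With the k deaths counted, S(t) = (1 − k/85) × S_rest(t) once they have occurred. If S_rest is exponential with median m, the corrected median is m × [1 + log2(1 − k/85)]. The values of m are illustrative; the documents give none.

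| k | Curve just after day 21, rule → corrected | m = 3 months | m = 6 months | m = 9 months |
|---|---|---|---|---|
| 1 | 100% → 98.8% | 2.95 | 5.90 | 8.85 |
| 3 | 100% → 96.5% | 2.84 | 5.69 | 8.53 |
| 5 | 100% → 94.1% | 2.74 | 5.48 | 8.21 |

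The 100% holds because no other patient has an assessed deterioration before day 22 in this layout. A numerical Kaplan-Meier on 85 patients, with the early deaths at day 14 and m = 6, agrees: the median falls from 179 to 173 days for k = 3 and from 179 to 167 days for k = 5.

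**5. Effect on the count.** The number with deterioration or death rises by k, and the percentage by k/85: 1.2, 3.5 or 5.9 points for k = 1, 3 or 5.

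**6. Against sampling error.** With 85 uncensored patients, the standard error of S at the median is √(0.25/85) = 0.054, a 95% band of 0.394 to 0.606. On a 6-month exponential curve those levels are reached at −6 × log2(0.606) = 4.3 and −6 × log2(0.394) = 8.1 months. A shift from 6.0 to 5.5–5.9 months lies well inside that range.

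**The case against.** The strongest objection is that the PRO rule is internally consistent. Death counts only in relation to an assessment where change could be evaluated. A patient with no follow-up questionnaire has no such assessment, so Day-1 censoring follows. A reader might infer a flat contradiction between event and censoring rules; the full death sentence does not support that. What stands is narrower: the rule departs from the any-cause-death intent of the endpoint and from the PFS rule, and no reason is given.

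One could also read baseline as the last usable assessment, which would make these deaths events. The wording is against this, since missing baseline data is listed as a separate case and change cannot be evaluated at baseline. If the reading is arguable, two programmers could code the rule differently, and the text still needs repair.

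On size, the objection largely succeeds. The exponential figures are better seen as an upper scenario for the cited trial population, and the 12-week life-expectancy criterion (Protocol 5.1) should lower early deaths further. Poorer-prognosis patients may push the other way. Week-6 shares are higher (7.1% under the exponential with median 13.0 months, 3.2% under the Weibull), but they apply in full only if everyone who died in weeks 3 to 6 also missed the Cycle 2 questionnaire. With deterioration seen only at 3-weekly visits, the median may not move at all. The time-to-deterioration summaries are planned only if feasible, and OS reports every death separately.

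A reader might also infer that the loss falls mainly on performance status 2 patients. That is plausible, but the documents give no early-death or questionnaire-completion figure by performance status, so it cannot be claimed.

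**Conclusion.** The point holds as an inconsistency with a known direction and a probably small effect. As written, the earliest deaths leave the risk set and count as non-events, so time to deterioration is biased upwards.

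About 1 to 3 of 85 patients would be affected under the survival assumptions closest to the cited durvalumab data, and about 6 of 85 with a 7-month median. On an assumed 6-month median, 1 to 5 such deaths take off about 0.1 to 0.5 months. These sizes rest on the assumed survival shapes, on n = 85, on every patient having a baseline score, and on counting only deaths before the Cycle 2 questionnaire.

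The primary safety endpoints are not touched, and no formal hypothesis depends on this. It still merits correction, because it biases a set of reported curves in the favourable direction and is easily put right.

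**What to change.** Make the same two changes in SAP 4.2.2.2 and in both places in Protocol 9.5.2.3. Changing the censoring sentence alone would leave it in conflict with the restriction on death.

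- **Death sentence:** count death as an event if it occurs within 2 visits of the last evaluable PRO assessment, or within 2 visits of baseline if there is no evaluable post-baseline assessment.
- **Censoring sentence:** 'Patients without baseline data are censored at Day 1. Patients with baseline data but no evaluable post-baseline visit are censored at Day 1 unless death occurs within 2 visits of baseline; that death is then an event on the date of death.'

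Keeping patients without a baseline score outside the exception matters, because a window counted from baseline has no anchor for them. In the SAP the censoring paragraph sits under symptom deterioration but is worded for QoL/function, so state that it covers both, and the QLQ-LC13.

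Report the number censored at Day 1 by reason: no baseline data, or no evaluable follow-up.

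The cost is a few lines of text and a small programming change. Dates of death are already collected for OS, so no new data are needed.

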For each of the symptoms scales/items in the EORTC QLQ-C30 questionnaire, time to symptom deterioration will be defined as the time from start of study drug until the date of the first clinically meaningful symptom deterioration (an increase in the score from baseline of ≥ 10 points) that is confirmed at the subsequent assessment (at least 14 days apart) or death (by any cause) in the absence of a clinically meaningful symptom deterioration, regardless of whether the patient withdraws from study drug or receives another anticancer therapy prior to symptom deterioration. Death will be included as an event only if the death occurs within 2 visits of the last PRO assessment where the symptom change could be evaluated.

Patients with a single deterioration and no further assessments will be treated as deteriorated in the analysis. Patients whose symptoms (as measured by EORTC QLQ-C30) have not shown a clinically meaningful deterioration and who are alive at the time of the analysis will be censored at the time of their last PRO assessment where the symptom could be evaluated. Also, if symptoms deteriorate after 2 or more missed PRO assessment visits or the patient dies after 2 or more missed PRO

assessment visits, the patient will be censored at the time of the last PRO assessment where the symptom could be evaluated. If a patient has no evaluable visits or does not have baseline data, he/she will be censored at Day 1.

The analysis of time to symptom deterioration will be done with a subset of patients who have baseline scores of ≤ 90 .

Time to quality of life/function deterioration

For QoL, time to deterioration will be defined as the time from start of study drug until the date of the first clinically meaningful deterioration (a decrease in the function scales or the global health status/QoL from baseline of ≥ 10 points) that is confirmed at the subsequent assessment (at least 14 days apart) or death (by any cause) in the absence of a clinically meaningful deterioration, regardless of whether the patient withdraws from study drug or receives another anticancer therapy prior to QoL/function deterioration. Death will be included as an event only if the death occurs within 2 visits of the last PRO assessment where the QoL/function change could be evaluated.

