## 3. ANALYSIS SETS

### 3.1 Intention to treat (ITT) population

Intention to treat (ITT) population consisted of all enrolled patients who had received at least 1 dose of study drug (chemotherapy or Durvalumab).

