##### Endpoints analyzed:

- Change from baseline in European Organisation for Research and Treatment of Cancer Quality of Life Questionnaire Core 30 items (EORTC QLQ-C30):

This analysis will be performed for the Intention-to-Treat population (ITT). For the following endpoints, change from baseline is defined as the post-treatment value minus the value at baseline. The % change from baseline will be calculated as:

$$(\text{Postbaseline value} - \text{baseline value}) / \text{baseline value} \times 100.$$

The **EORTC QLQ-C30 v3 questionnaire** is included for the purpose of assessing HRQoL and is a well-established measure of HRQoL/health status. It assesses HRQoL/health status through 9 multi-item scales: 5 functional scales (physical, role, cognitive, emotional, and social), 3 symptom scales (fatigue, pain, and nausea and vomiting), and a global health and quality-of-life (QoL) scale. Six single-item symptom measures are also included dyspnea, insomnia, appetite loss, constipation, diarrhea, and financial difficulties. For each of the 15 domains, final scores are transformed such that they range from 0 to 100, where higher scores indicate greater functioning, greater HRQoL, or greater level of symptoms .

The principle for scoring these scales is the same in all cases:

- Estimate the average of the items that contribute to the scale; this is the raw score.
- Use a linear transformation to standardise the raw score, so that scores range from 0 to 100; a higher score represents a higher ("better") level of functioning, or a higher ("worse") level of symptoms.

For all scales, the *RawScore*, *RS*, is the mean of the component items:

$$\text{RawScore} = \text{RS} = (I_1 + I_2 + \dots + I_n)/n$$

Then for **Functional scales**:

$$\text{Score} = \left\{ 1 - \frac{(\text{RS} - 1)}{\text{range}} \right\} \times 100$$

For **Symptom scales/ items** and **Global health status/ QoL**:

$$\text{Score} = \left\{ \frac{(\text{RS} - 1)}{\text{range}} \right\} \times 100$$

The following outcomes will be analysed for this endpoint:

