- Quality of life/function improvement rate: defined as the number (%) of patients with 2 consecutive assessments at least 14 days apart that show a clinically meaningful improvement (an increase from baseline score  $\geq 10$  points for EORTC QLQ-C30 functional scales and global health status/QoL) in that scale from baseline.
- Change from baseline in European Organisation for Research and Treatment of Cancer Quality of Life. Questionnaire-Lung Cancer 13 (EORTC QLQLC13):

This analysis will be performed for the Intention-to-Treat population (ITT). For patients with SCLC, a disease-specific 13-item self-administered questionnaire for lung cancer was developed to be used in conjunction with the EORTC QLQ-C30. It comprises both multi-item and single-item measures of lung cancer-associated symptoms (i.e., coughing, haemoptysis, dyspnoea, and pain) and side effects from conventional

chemotherapy and radiotherapy (i.e., hair loss, neuropathy, sore mouth, and dysphagia). Similar to the EORTC QLQ-C30, all questions except one have a 4-point scale: (not at all, a little, quite a bit and very much). One question (no. 43, —Did you take any medicine for pain?) has a response option (Yes; No). The scoring approach for the EORTC QLQ-LC13 is similar to the EORTC QLQ-C30.

The following outcomes will be analysed for this endpoint:

- Time to symptom deterioration
- Symptom improvement rate

- Changes from baseline in PRO-CTCAE:

The **PRO-CTCAE** is included to address tolerability from the patients' perspective. It was developed in recognition that collecting symptom data directly from patients using PRO tools can improve the accuracy and efficiency of symptomatic AE data collection.

In this study, only items that are considered relevant for the study, site of cancer, and cancer treatment are selected.

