## **5. ANALYSIS METHODS**

Descriptive statistics will be used for all variables, as appropriate. Continuous variables will be summarized by the number of observations, mean, standard deviation, median, quartiles (Q1 and Q3), minimum, and maximum. Categorical variables will be summarized by frequency counts and percentages for each category. The number of missing data will be provided for every analysed variable.

Missing values will not be considered for calculating percentages or any other descriptive, meaning that only valid values will be presented. No use of any method for the handling of missing data is foreseen.

For patients excluded from the statistical analyses, descriptive of the reasons for non-evaluability will be provided.

The software package SAS version 9.4 will be used for data analysis.

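### Symptom and function improvement rates set no baseline-score condition, so patients who cannot improve by 10 points appear to count as non-improvers

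*SAP*

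**What the plan says.** SAP 4.2.2.2 defines two improvement rates for the QLQ-C30. The first reads "Symptom improvement rate: defined as the number (%) of patients with 2 consecutive assessments at least 14 days apart", with a change of 10 points or more from baseline. The second has the same structure: "Quality of life/function improvement rate: defined as the number (%) of patients with 2 consecutive assessments at least 14 days apart". The symptom rate is also listed for the QLQ-LC13.

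On the population, the same section says of each questionnaire: "This analysis will be performed for the Intention-to-Treat population (ITT"). SAP 3.1 defines that population: it "population consisted of all enrolled patients who had received at least 1 dose of study drug (chemotherapy or Durvalumab"). SAP 5 gives the only general rule on percentages: "Missing values will not be considered for calculating percentages or any other descriptive, meaning that only valid values will be presented". SAP 6.2 repeats it. On method, SAP 5.2.2 says no more than: "Symptom improvement rate and Quality of life / function improvement (defined in 4.2.2) will be summarized".

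Protocol 9.5.2.3 defines the same two rates, also without a baseline condition. For one related endpoint it does set such a condition: "The analysis of time to symptom deterioration will be done with a subset of patients who have baseline scores of" 90 or less. The SAP does not carry that restriction over.

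The documents disagree on direction. The symptom improvement rate is a decrease of at least 10 points in Protocol 9.5.2.3 and an increase in SAP 4.2.2.2. The SAP's own scoring (4.2.2.2 and 5.2.2) makes a higher symptom score worse.

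**The concern.** A score bounded at 0 and 100 leaves some patients no room for a 10-point improvement. A patient without haemoptysis at baseline cannot report less of it. Such patients have valid data, so the missing-value rule does not remove them. They can never enter the numerator, and they appear to remain in the denominator.

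The percentage then mixes two things: how many patients had room to improve, and how many of those did. Two symptoms with the same rate among affected patients could show quite different figures only because one is less common at baseline. From the percentage alone, a reader could not tell a symptom that was absent from one that was present and did not improve.

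**Working it through.** **Inputs from the documents.** Score range 0 to 100 and the scoring formulas (SAP 4.2.2.2). Threshold of 10 points (SAP 5.2.2, Protocol 9.5.2.3). Four response levels per item (SAP 4.2.2.2). Planned size about 85 (SAP 2.1). Direction of symptom improvement taken as a decrease (Protocol 9.5.2.3), because it agrees with the SAP's scoring.

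**Assumptions.** The share unable to improve, f, is not given and will differ by scale; it is varied from 10% to 90%. The rate among patients able to improve is set at 50% for illustration. Where the documents do not show them, item counts and the 7-point format of the global scale are also assumed.

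**Check of the interval method.** The plan states no improvement rate, so there is no figure for this endpoint to reproduce. Exact Clopper-Pearson intervals at n = 85 were checked against the precision table in Protocol 9.2. Counts of 17, 21, 51 and 60 give 12.1–30.1, 16.0–35.3, 48.8–70.5 and 59.7–80.0, which match the printed intervals.

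**Step 1: which baselines rule out improvement.** With k items at four levels, the score moves in steps of 100/(3k).

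- Symptoms, where improvement is a fall of at least 10: one, two or three items give steps of 33.3, 16.7 and 11.1, so only a baseline of 0 is excluded. On a single item this is every patient who answers at the lowest level.
- Function, where improvement is a rise of at least 10: two or three items exclude only 100. Four items (step 8.3) exclude 91.7 and 100. Five items (step 6.7) exclude 93.3 and 100.
- Global scale, two 7-point items (step 100/12 = 8.3): excludes 91.7 and 100.

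All of these fall under one rule: symptom baseline below 10, or function or global baseline above 90.

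**Step 2: effect on the rate.** Reported rate = (1 − f) × rate among patients able to improve. Its ceiling is 1 − f. With 85 patients, and counts rounded to whole patients:

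| f | Able to improve | Improved | Rate over all 85 (95% CI) | Rate over those able (95% CI) | Ceiling over all 85 |
|---|---|---|---|---|---|
| 10% | 76 | 38 | 44.7% (33.9–55.9) | 50.0% (38.3–61.7) | 89.4% |
| 30% | 59 | 30 | 35.3% (25.2–46.4) | 50.8% (37.5–64.1) | 69.4% |
| 50% | 42 | 21 | 24.7% (16.0–35.3) | 50.0% (34.2–65.8) | 49.4% |
| 70% | 26 | 13 | 15.3% (8.4–24.7) | 50.0% (29.9–70.1) | 30.6% |
| 90% | 8 | 4 | 4.7% (1.3–11.6) | 50.0% (15.7–84.3) | 9.4% |

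**Step 3: dependence on direction.** Under the SAP's literal wording, symptom improvement is an increase. The symptom baselines that rule it out would then be those above 90, and a patient at 0 could count as improved by getting worse. Some patients cannot meet the criterion under either wording, but which ones depends on the direction.

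**The case against.** **The denominator is inferred.** No sentence states it. The ITT statement points to all treated patients, and the missing-value rule may remove some. This stands, and it is why the point says that these patients appear to remain. Nothing in the SAP would take them out.

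**An all-treated rate is legitimate.** The study has one arm, no hypothesis (Protocol 9.1) and no comparison drug (SAP 4.1.3). The share of all treated patients with confirmed improvement is a valid descriptive figure if labelled as such. This stands too, and it is a reason to keep that rate beside the other one.

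**The Protocol's precedent is narrow.** A reader might infer that the Protocol restricts every deterioration endpoint to patients who can worsen, so that improvement merely lacks the mirror rule. The restriction covers time to symptom deterioration only. Function and quality-of-life deterioration have none, although a score below 10 cannot fall by 10. The precedent supports the principle for symptoms; for function the argument rests on the arithmetic alone.

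**Benefit is not hidden.** A reader might infer that improvement in symptomatic patients would be invisible. SAP 5.2.2 also reports original values and changes by visit for the QLQ-C30 symptom scales/items, the global score and the functional domains, and SAP 5 gives their quartiles and range. A heavy floor or ceiling would show there, though not the exact number able to improve.

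**Conclusion.** The point holds as a matter of interpretation. As written, the improvement rates appear to be scaled down by (1 − f), by an amount that differs between scales and is not reported. Under the illustrative assumptions (85 patients, 50% among those able to improve), the rate is 44.7% at f = 10% and 24.7% at f = 50%.

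A reader might go further and say that the rates would mainly reflect how many patients had each symptom at baseline. That follows only where f is large, and the documents give no f for any scale. At f = 10% the gap is about 5 percentage points.

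No primary endpoint, test or sample-size figure is touched. The symptom half of the point also depends on settling the direction of improvement in favour of a decrease.

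**What to change.** 1. Correct SAP 4.2.2.2 first, so that symptom improvement is a decrease of at least 10 points, in line with the SAP's scoring and the definition in Protocol 9.5.2.3. Until this is done, a rule of baseline ≥10 would drop patients who can meet the SAP's criterion and keep those above 90 who cannot. The SAP's definition of time to symptom deterioration (a decrease) and the symptom row of the Protocol's visit-response table (a rise counted as improvement) have the same reversal and should be aligned at the same time.
2. State the denominators: baseline ≥10 for symptom scales and items, and ≤90 for function scales and global quality of life.
3. Show the number eligible beside each rate, and give the all-ITT rate alongside, labelled as such.

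This needs SAP wording and table shells but no new data. The downside is smaller denominators and wider intervals for uncommon symptoms: at f = 70% the interval runs from 29.9% to 70.1% on 26 patients.
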